X-ray is conducted at Week 4, or when simple X-ray and bone scintigraphy are conducted at Week 8, during observation period, and Week 48 (completion of observation period), date of examination and assessment findings (improvement, unchanged, aggravation of bone morphology, trabecular bone structure and other abnormal findings by simple X-ray, compared with baseline) should be recorded.

When CT and MRI is conducted at baseline, record the findings.

(6) Adverse events

Record the name of an adverse event that developed after the baseline and before completion of observation period, date of onset, seriousness, action taken, outcome, and causal relationship with this drug to be evaluated. Follow up adverse events until recovery as best as possible.

(7) Laboratory test

Conduct general hematology, blood chemistry, and urinalysis at baseline and during observation period and record the test item assessed as abnormal variation compared with baseline in the adverse events section of CRF. Record the laboratory test data of the item assessed as abnormal variation in “Variation of laboratory test data assessed as abnormal variation” section.

8. Items and method of analysis

(1) Analysis population

Conduct analysis for all patients administered this drug.

Conduct analysis of the patients above according to the baseline demographics and pathology.

(2) Demographic factors

Tabulate patients by sex, age, weight, morbid period, prior therapy, concomitant drugs.

(3) Efficacy endpoint

1) Serum ALP, bone metabolism markers

i) Serum ALP

Calculate summary statistics (mean, standard deviation, minimum, maximum) and 95% confidence interval for the excess serum ALP measured at baseline, Week 4, Week 8, during observation period, and Week 48. Conduct one-sample t-test for percent change in excess serum ALP. Show time-course of change at baseline, Week 4, Week 8, during observation period, and Week 48.

*Excess serum ALP: actual value of serum ALP — (maximum of reference value + minimum of reference value)/2

ii) Bone metabolism marker

Calculate the mean and standard deviation for the values measured before and after administration. Conduct one-sample t-test for percent change.

2) Tabulation of pain associated with osseous Paget's disease

Show distribution of pain severity at each time point of baseline, Week 4, Week 8, during observation period, and Week 48.

3) Treatment compliance

Conduct frequency tabulation for treatment compliance during treatment period.

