(4) Safety endpoints

Conduct frequency tabulation for the type and seriousness of treatment-related adverse events.

9. Organization for conducting survey

Responsible person for surveillance

PPD

10. In case of contracting a part of survey duties, name and address of the party that contracted the concerned duty and scope of the contracted duty

PPD

11. Other necessary items

(1) Revision of survey plan

In case a partial change in Dosage and Administration or Indications is approved during the period of this surveillance, necessity for revision of the protocol should be reviewed when necessary.

(2) Actions taken in case of occurrence of a problem or question

In case any problem is found with safety or efficacy, implementation of a special drug use surveillance should be reviewed to detect or confirm the factor or to review a presumed item.

12. Reference

1) Jun Hashimoto, et al.: Prevalence and clinical characteristics of osseous Paget's disease in Japan
Osteoporosis Japan 15 241-245, 2007

Benet 17.5 mg Tablets Special Drug Use Surveillance in Patients With Osseous Paget's Disease
(All-case Surveillance)
—48-week Surveillance—
Protocol Version 2

Prepared on April 1, 2015

1. Background and purpose of surveillance

Osseous Paget's disease is a very rare disease in Japan and available drugs are limited compared with Europe and the U.S. Benet 17.5 mg Tablets (this drug) was designated as an orphan drug and developed for treatment of osseous Paget's disease. During development, patients with osseous Paget's disease were surveyed for 40 weeks after oral administration of one tablet of this drug once daily for 8 consecutive weeks (total of 48 weeks). High level of serum alkaline phosphatase (serum ALP) that indicates abnormal acceleration of bone metabolism turnover, was lowered and maintained during the observation period. With respect to safety, a serious adverse event was observed in one patient (recurrent cholangiocarcinoma) but causal relationship was denied. However, osseous Paget's disease is rare disease in Japan and only a very limited number of patients (12 patients) were reviewed.

The purpose of this special drug use surveillance (8-week treatment period) is to evaluate the safety and efficacy of this drug administered once daily (one tablet per dose) in patients with osseous Paget's disease for 48 weeks from baseline in daily medical practice.

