		
• 5.(4)9) correction of treatment compliance• 5.(5)1) correction of changes in excess serum ALP• 5.(5)2) correction of changes in excess serum ALP (subgroup analysis)• 5.(5)4) correction of changes in serum ALP• 5.(5)5) correction of changes in serum ALP (subgroup analysis)

Table of Contents

1. Purpose of analysis	1
2. Patients to be included in analyses	1
(1) Breakdown of patients to be included in analyses	1
(2) Patients included in safety evaluation	1
(3) Patients included in efficacy evaluation	1
3. Handling of patients	1
4. Data Lock Point	2
(1) Data Lock Point	2
5. Tabulation and analysis at each DLP	2
(1) Patient composition diagram	2
(2) Details of patients excluded from safety evaluation and patients excluded from efficacy evaluation	2
(3) Details of discontinued/dropout patients	3
(4) Safety analysis	3
(5) Efficacy analysis	9
(6) Analysis of patients excluded from safety evaluation	13
(7) List of summary of surveyed patients (Attachment form 3)	13
(8) Other arrangements	13

Terminology

Term	Explanation
Adverse event	All events recorded in [Adverse events] section of CRF. All untoward medical events encountered in a patient administered a medication (including abnormal laboratory data and infections). A causal relationship with this drug is not always clear.
Adverse drug reaction	Adverse events with “causal relationship with this drug” in [Adverse events] section of case report form (CRF) other than “not related”. However, an adverse event judged by the investigator as “not related” but judged by the sponsor as “related” is handled as an adverse drug reaction.
Serious adverse event	Adverse event for which “seriousness” in [Adverse events] section of CRF is “serious”. However, an adverse event judged by the investigator as “non-serious” but judged by the sponsor as “serious” is handled as a serious adverse drug reaction. Also, adverse events listed in the implementation guide as an “adverse event to be always judged serious” and “Takeda Medically Significant AE List” are included as well.

1. Purpose of analysis

To determine tabulation and analysis that are conducted for preparation of the documents for application for reexamination and a periodic safety report in the survey conducted for the following purpose.

[Purpose of survey]

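### Non-serious adverse events that investigator and sponsor both judge unrelated have no frequency table in the safety population

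*Protocol*

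**What the plan says.** **Collection is broad.** Protocol 7.(6) instructs: "Record the name of an adverse event that developed after the baseline and before completion of observation period", together with onset date, seriousness, action taken, "outcome, and causal relationship with this drug to be evaluated". For laboratory tests, Protocol 7.(7) tells the investigator to "record the test item assessed as abnormal variation compared with baseline in the adverse events section of CRF". Causality does not limit what is recorded.

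**Planned analysis is narrow.** Protocol 8.(4) contains a single instruction: "Conduct frequency tabulation for the type and seriousness of treatment-related adverse events".

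**The SAP defines three classes.** In its Terminology table (Version 4.1), an adverse event is "All events recorded in [Adverse events] section of CRF", with the remark "A causal relationship with this drug is not always clear". An adverse drug reaction is any event whose causality entry is something other than not related. An event that the investigator calls unrelated "but judged by the sponsor as “related” is handled as an adverse drug reaction". Serious events are those the investigator rates serious, those the sponsor upgrades, and those on an always-serious list or the sponsor's medically significant list. The serious class carries no causality condition.

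**The concern.** The survey has no comparator, and causality is judged case by case by people who know the treatment. In that setting a causality filter largely determines which events are counted. A common, non-specific event that each physician ascribes to age or disease may form a pattern that shows only in aggregate.

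The protocol's purpose is to evaluate safety over 48 weeks in daily practice, because only 12 patients were reviewed during development. Non-serious laboratory changes pass through the same filter, since the SAP plans no separate laboratory summary. So does the search for risk factors: the tests in SAP 5.(4)5) and the stratified analysis in 5.(4)6) both start from presence or absence of an adverse drug reaction.

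**Working it through.** No arithmetic from the plan bears on this. The check is to take every output in SAP Version 4.1 that reports events and sort it by the class of event it covers.

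| SAP output | Event class | Patients | Form |
|---|---|---|---|
| 5.(2) | Any adverse event, by name | Excluded from safety or efficacy evaluation | Listing |
| 5.(3) | Any adverse event, by name | Discontinued/dropout, CRF collected | Listing |
| 5.(4)2) | Adverse drug reactions (and infections, on a ministry form cited but not reproduced) | Safety population | Frequency |
| 5.(4)3) | Serious adverse events, any causality | Safety population | Frequency |
| 5.(4)4), 5), 6) | Adverse drug reactions | Safety population | Frequency |
| 5.(4)7) | Adverse drug reactions | Re-administered patients in the safety population | Per patient |
| 5.(4)10), 11) | Serious, and unforeseeable, adverse drug reactions | All sources, including outside this survey | Frequency |
| 5.(6)1), 2) | Adverse drug reactions | Excluded from safety evaluation | Frequency |
| 5.(7) | Adverse drug reactions | All with a CRF | Listing |

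Count:

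- Based on adverse drug reactions: 7 in 5.(4) [items 2, 4, 5, 6, 7, 10, 11] + 2 in 5.(6) + 1 in 5.(7) = 10.
- Serious adverse events of any cause: 1.
- Listings of any adverse event: 2.
- Total: 10 + 1 + 2 = 13. Frequency tables of all adverse events: 0.

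Next, follow one event through the definitions. Suppose a laboratory change is recorded as an adverse event.

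1. If the investigator enters anything but not related, it is an adverse drug reaction and is tabulated.
2. If the investigator says not related but the sponsor says related, it is an adverse drug reaction and is tabulated.
3. If the investigator rates it serious, the sponsor upgrades it, or it is on either list, it enters the serious class and is tabulated. (The Terminology entry says a sponsor upgrade is handled as a serious adverse drug reaction rather than a serious adverse event. On either reading it is tabulated.)
4. If none of these applies, no frequency table contains it. It is named only if the patient is excluded from safety or efficacy evaluation, or is discontinued/dropout.

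The listings in step 4 reach part of the safety population. Under SAP 2.(3), patients excluded only from efficacy evaluation remain in it, and discontinued/dropout patients may as well. For a patient who is in both evaluation sets and did not discontinue or drop out, none of the thirteen outputs shows a step-4 event.

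One further input bears on the remedy. SAP 3 counts a re-administered person once per CRF unless patient unit is specified. A person with an initial course and two re-administrations adds three to the denominator, so an exact binomial interval on CRFs would treat three correlated courses as three independent patients.

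**The case against.** The best case for the plan has four parts. The physician's view is not final, because the sponsor can reclassify an event as related or serious. The adverse drug reaction class is inclusive, and the serious class is widened by two lists. The core tables follow prescribed ministry forms for re-examination and periodic reporting, and protocol and SAP agree with each other. Finally, an all-cause count without a comparator or reference rate cannot show an excess.

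All of this stands, and it narrows the point. It does not remove the residual class in step 4, and nothing in the documents prevents an added table. The last argument limits what the table can claim, but describing incidence is still part of evaluating safety.

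A reader might go further in several ways that the documents do not support:

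- *Everything the treating physician calls unrelated is lost.* The sponsor override and the widened serious class contradict this.
- *Such events leave no trace.* SAP 5.(2) and 5.(3) list the names of all adverse events for excluded and discontinued/dropout patients.
- *Unrelated serious events are hidden.* The one serious event in development, recurrent cholangiocarcinoma judged unrelated, is of a kind that SAP 5.(4)3) would show.
- *A given share of events is missing.* The documents give no proportion judged unrelated, so any percentage would be a guess.

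**Conclusion.** The point holds in narrow form. Non-serious adverse events, including abnormal laboratory changes recorded as such, have no frequency table in the safety population when investigator and sponsor both judge them unrelated and they are on neither list. Their names appear only in the listings of excluded and discontinued/dropout patients.

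This is a stated analysis choice. It is neither an internal contradiction nor a miscalculated table. Its extent is structural, at 0 of 13 event outputs, and the number of events affected cannot be derived from the documents. The conclusion assumes that the cited ministry forms and the two seriousness lists, none of which is reproduced, do not already require an all-cause table. The change is a cheap improvement to reporting, not a correction on which the survey's validity depends.

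**What to change.** - Add one table to SAP 5.(4), next to the adverse drug reaction table in 5.(4)2): all adverse events by SOC and PT regardless of causality, split by seriousness and by administration category.
- Give counts per CRF and by patient unit. Compute any exact 95% confidence interval on the patient unit only.
- State with the table that it describes incidence and does not by itself establish an excess.
- Amend Protocol 8.(4) so that the frequency tabulation covers adverse events as well as treatment-related adverse events.

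The cost is one extra table from data already in the CRF, and MedDRA coding of any events not yet coded. No data collection or clinical procedure changes.

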Ver. 1.3	April 9, 2010	
Revision for the fourth periodic safety report.
 
 • Change of terms (change from patients included in safety data analysis to patients included in safety evaluation, patients included in efficacy data analysis to patients included in efficacy evaluation) • 5.(4)3) addition of a list of seriousness, date of onset, outcome of adverse drug reactions • 5.(4)4) addition of onset of adverse drug reactions by patient demographics • 5.(4)5) addition of a list of onset of adverse drug reactions by patient demographics • 5.(4)6) addition of a list of seriousness, date of onset, outcome of adverse drug reactions by patient demographics • 5. (5) addition of analysis of patients excluded from safety evaluation
Ver. 2.0	July 7, 2010	
 • Addition of efficacy analysis • Addition of 7.(7) “Excess serum ALP”
Ver. 2.1	April 1, 2011	
 • Table (2) “presence or absence of concomitant drug for osseous Paget’s disease” and “other concomitant drugs” were combined as “concomitant drugs”. The same for breakdown. • 5.(5)8) deletion of test of imaging diagnosis. • 5.(7)3) deletion of conversion method for days.
Ver. 2.2	July 19, 2011	
 • 5.(4)1) addition of administration category and administration period category to a list of onset of adverse drug reactions/ infections • 5.(4)3) addition of administration category and administration period category to a list of seriousness, date of onset, outcome • Table (2) addition of “age 2” to patient demographics, addition of “administration period 2”, addition of “unknown” to “age” category. • Table (2) change in category of “administration period (cumulative)” in patient demographics • 5.(4)7) addition of comparison of adverse drug reaction profile after the

Version No.	Date of preparation/revision	Site/reason for change
		
initial administration and re-administration 1 in individual patients.
 
 • 5.(4)8) addition of summary of re-administration intervals • 5.(5)1) addition of creation of a graph showing changes in percent change and a graph showing changes over time in each patient, of a graph showing changes over time by number of administration in patients who received re-administration, of summary of initial administration and transition in re-administered patients, and of a comparison table of measured values at the initial administration and re-administration 1 and percent change to changes in excess serum ALP. • 5.(5)3) addition of changes in excess serum ALP (subgroup analysis 2) • 5.(5)4) addition of creation of a graph showing changes in percent change and a graph showing changes over time in each patient, of a graph showing changes over time by number of administration in re-administered patients, a summary of initial administration and transition in re-administered patients, and a comparison table of measured values at the initial administration and re-administration 1 and percent change to changes in serum ALP • 5.(5)6) addition of changes in serum ALP (subgroup analysis 2) • 5.(8)7) addition of handling of re-administered patients • 5.(8)8) addition of calculation method for re-administration intervals • 5. overall, renumbering of Form number
Ver. 2.3	April 5, 2013	
 • 4.(1) change in Data Lock Point • 5.(7)5) addition of the following data at evaluation time point: i) acceptable range at each time point; ii) data of Nth administration when a patient received (N+1)th administration.
Ver. 2.4	July 5, 2013	
 • 2.(3) correction of efficacy analysis population • 4.(1) change in Data Lock Point • 5.(1) addition to patient composition diagram • 5.(5)10) addition to imaging findings
Ver. 2.5	March 20, 2015	
 • 5.(5)2) addition to changes in excess serum ALP (subgroup analysis)
Ver. 2.6	March 25, 2016	
 • 4.(1) change in Data Lock Point
Ver. 2.7	June 2, 2016	
 • 5.(1) correction of patient composition diagram. • 5.(4)3) correction of a creation method for a list of seriousness, date of onset, outcome of adverse drug reactions • 5.(4)4) correction of title of onset of adverse drug reactions by factors, number of digit of p-value, output method for “unknown (no entry)”, and errors • 5.(4)5) correction of title and creation method of onset of adverse drug reactions <stratified analysis>

Version No.	Date of preparation/revision	Site/reason for change
		
 5.(4)6) correction of title and creation method for a list of seriousness, date of onset, outcome of adverse drug reactions by factors
Ver. 3.0	May 17, 2017	
 consistency of terminology “group” → “patients” 2.(2) modification of description of patients included in safety evaluation 2.(3) modification of description of patients included in efficacy evaluation 5.(1) modification of description of patient composition diagram 5.(2) modification of detailed description of patients excluded from safety evaluation and patients excluded from efficacy evaluation 5.(3) modification of detailed description of discontinued/dropout patients, and addition of specification of “unknown” “no entry” 5.(4)1) modification of list of onset of adverse drug reactions/infections (Separate form 2 of the notification of director of MHLW) and addition of number of the same patients, occurrences of same adverse drug reactions/infections 5.(4)2) modification of description in the list of onset of serious adverse events (Separate form 2-2 of the notification of director of MHLW) and addition of number of the same patients, occurrences of same adverse drug reactions/infections 5.(4)4) modification of description of onset of adverse drug reactions by factors 5.(4)7) modification of description of comparison of adverse drug reaction profile after initial administration and re-administration 1 in individual patients 5.(5) correction of “difference before and after administration” to “percent change” in efficacy analysis 5.(5)1) modification of description of changes in excess serum ALP 5.(5)2) modification of description of changes in excess serum ALP (subgroup analysis) 5.(5)3) modification of description of changes in excess serum ALP (subgroup analysis 2) 5.(5)4) modification of description of changes in serum ALP 5.(5)6) modification of description of changes in serum ALP (subgroup analysis 2) 5.(5)7) modification of description of changes in bone metabolism markers
Ver. 4.0	February 7, 2018	
 Addition of terminology 1. addition of application for re-examination to the purpose of analysis 2.(2) correction of patients included in safety evaluation 3. correction of handling of patients

Version No.	Date of preparation/revision	Site/reason for change
		
 • 4. (1) addition of date of starting survey to Data Lock Point, additions to the 12th and 13th Data Lock Points • 5.(4)1) addition of patient demographics • 5.(4)2) modification of description of a list of onset of adverse drug reactions/infections (Separate form 2 of the notification of director of MHLW), addition of tabulation by patient unit • 5.(4)3) modification of description of a list of onset of serious adverse events (Separate form 10 of the notification of director of MHLW), addition of tabulation by patient unit • 5.(4)4) modification of description in the list of seriousness, date of onset, outcome of adverse drug reactions, addition of priority of category items • 5.(4)5) correction of onset of adverse drug reactions by factors • 5.(4)6) deletion of a list of seriousness, date of onset, outcome of adverse drug reactions by factors • 5.(4)7) correction of adverse drug reaction profile after initial administration and re-administration in individual patients • 5.(4)9) addition of treatment compliance • 5.(4)10) addition of profile table of serious adverse drug reactions • 5.(4)11) addition of profile table of adverse drug reactions not foreseeable from “Precautions”. • 5.(5)1) modification of description of changes in excess serum ALP • 5.(5)2) correction of changes in excess serum ALP (subgroup analysis) • 5.(5)3) correction of changes in excess serum ALP (subgroup analysis 2) • 5.(5)4) modification of description of changes in serum ALP, addition of tabulation of percentage • 5.(5)5) correction of changes in serum ALP (subgroup analysis) • 5.(5)6) correction of changes in serum ALP (subgroup analysis 2) • 5.(5)8) deletion of changes in bone metabolism markers (subgroup analysis) • 5.(5)8) addition of tabulation by sites to evaluation of pain associated with osseous Paget’s disease • 5.(5)9) addition of other abnormal findings to imaging findings • 5.(7) addition of a list of summary of surveyed patients (Attachment form 3) • 5.(8)7) addition of handling of efficacy data to handling of patients receiving re-administration • 5.(8)9) addition of “tests” • 5.(8)10) addition of output of category “unknown”
Ver. 4.1	March 30, 2018	
 • 5.(4)2) correction of a list of onset of adverse drug reactions/infections (Attachment form 2 of the notification of Director of the MHLW)

Version No.	Date of preparation/revision	Site/reason for change
		
• 5.(4)9) correction of treatment compliance• 5.(5)1) correction of changes in excess serum ALP• 5.(5)2) correction of changes in excess serum ALP (subgroup analysis)• 5.(5)4) correction of changes in serum ALP• 5.(5)5) correction of changes in serum ALP (subgroup analysis)

Table of Contents

1. Purpose of analysis	1
2. Patients to be included in analyses	1
(1) Breakdown of patients to be included in analyses	1
(2) Patients included in safety evaluation	1
(3) Patients included in efficacy evaluation	1
3. Handling of patients	1
4. Data Lock Point	2
(1) Data Lock Point	2
5. Tabulation and analysis at each DLP	2
(1) Patient composition diagram	2
(2) Details of patients excluded from safety evaluation and patients excluded from efficacy evaluation	2
(3) Details of discontinued/dropout patients	3
(4) Safety analysis	3
(5) Efficacy analysis	9
(6) Analysis of patients excluded from safety evaluation	13
(7) List of summary of surveyed patients (Attachment form 3)	13
(8) Other arrangements	13

Terminology

Term	Explanation
Adverse event	All events recorded in [Adverse events] section of CRF. All untoward medical events encountered in a patient administered a medication (including abnormal laboratory data and infections). A causal relationship with this drug is not always clear.
Adverse drug reaction	Adverse events with “causal relationship with this drug” in [Adverse events] section of case report form (CRF) other than “not related”. However, an adverse event judged by the investigator as “not related” but judged by the sponsor as “related” is handled as an adverse drug reaction.
Serious adverse event	Adverse event for which “seriousness” in [Adverse events] section of CRF is “serious”. However, an adverse event judged by the investigator as “non-serious” but judged by the sponsor as “serious” is handled as a serious adverse drug reaction. Also, adverse events listed in the implementation guide as an “adverse event to be always judged serious” and “Takeda Medically Significant AE List” are included as well.

1. Purpose of analysis

To determine tabulation and analysis that are conducted for preparation of the documents for application for reexamination and a periodic safety report in the survey conducted for the following purpose.

[Purpose of survey]

To observe the efficacy and safety of BENET Tablets 17.5 mg/Actonel Tablet 17.5 mg in patients with osseous Paget's disease up to Week 48 as an all-case surveillance based on the approval conditions.

2. Patients to be included in analyses

(1) Breakdown of patients to be included in analyses

“Patients included in safety evaluation” and “patients included in efficacy evaluation”.

(2) Patients included in safety evaluation

Of the patients from whom a case report form (CRF) is collected, those who satisfy either of the following conditions are excluded from safety evaluation and others are included in safety evaluation.

- i) A patient not administered this drug
- ii) A patient in whom onset of adverse event is unknown
- iii) Of the patients with duplicated enrollment, those who were enrolled later.
- iv) A patient for whom administration was started outside the enrollment period*

* The date of starting administration falls after the enrollment period of January 31, 2016 (on and after February 1, 2016).

(3) Patients included in efficacy evaluation

Of the patients included in safety evaluation, those who satisfy the following conditions are excluded from efficacy evaluation and others are included in efficacy evaluation.

- i) patients from whom the information on efficacy before and after administration was not obtained.

3. Handling of patients

Unless otherwise specified, a patient recorded in a different CRF as a re-administered patient will be tabulated as one patient based on each CRF even if he/she is the same person. When tabulating the same patient as one patient, it should be clarified in “creation method” that tabulation is conducted for “each patient unit”.

4. Data Lock Point

(1) Data Lock Point

Date of starting survey: August 1, 2008

Data Lock Points (DLP) are shown below.

1st: September 30, 2008

2nd: March 31, 2009

3rd: September 30, 2009

4th: March 31, 2010

5th: March 31, 2011

6th: March 31, 2012

7th: March 31, 2013

8th: March 31, 2014

9th: March 31, 2015

10th: March 31, 2016

11th: March 31, 2017

12th: March 31, 2018, re-examination

13th: July 15, 2018, re-examination “(4) Safety analysis 10) Profile Table of serious adverse drug reactions,

11) Profile Table of adverse drug reactions not foreseeable from ‘Precautions’”

5. Tabulation and analysis at each DLP

(1) Patient composition diagram

<Analysis population>

Enrolled patients.

<Preparation method>

- 1) number of study sites
- 2) number of enrolled patients
- 3) number of patients from whom CRF was collected
- 4) number of patients included in safety evaluation
- 5) number of patients included in efficacy evaluation
- 6) patients from whom CRF was not obtained, patients excluded from safety evaluation, and patients excluded from efficacy evaluation

Tabulate the number of patients in 1) to 6) above. Tabulate the number of patients according to reasons for 6).

Of the patients from whom CRF was not obtained, output details in case other reason is applicable to a patient. Example) personal reason of a patient

(2) Details of patients excluded from safety evaluation and patients excluded from efficacy evaluation

<Analysis population>

Patients excluded from safety evaluation and patients excluded from efficacy evaluation.

<Preparation method>

Prepare a list of safety evaluation, efficacy evaluation, reason for exclusion, sex, age, date of starting administration of this drug, presence or absence of adverse event, and name of adverse events in order of patient number.

(3) Details of discontinued/dropout patients

<Analysis population>

Of the patients from whom CRF was collected, those who discontinued/dropped out.

<Preparation method>

Prepare a list of reason for discontinuation/dropout, safety evaluation, efficacy evaluation, sex, age, date of starting administration of this drug, date of discontinuation/dropout, presence or absence of adverse event, and name of adverse events in order of patient number. In case a reason for discontinuation/dropout is not known or specified, output as “unknown” and “no entry”, respectively.

(4) Safety analysis

1) Patient demographics

<Analysis population>

Patients included in safety evaluation.

<Preparation method>

Calculate the number of patients and percentage for each item of patient demographics in Table (1). Calculate summary statistics for items with *. Conduct tabulation by patient unit. In case of tabulation by patient unit, use the information of patient demographics of initial administration. **Table (1) Items of patient demographics**

Item	Category
Sex	1) M, 2) F, 3) unknown
Pregnancy (only for women)	1) not pregnant, 2) pregnant, 3) unknown
Age (years)*	1) <65, 2) ≥65, 3) unknown
Height (cm)*	-
Weight (kg)*	-
Dosing category ^{*1}	1) initial administration, 2) re-administration
Dosing period (days)	1) ≤56 days, 2) ≥57 days, 3) unknown
Treatment category	1) outpatient, 2) inpatient, 3) outpatient ⇔ inpatient, 4) unknown
Diagnosis name (Osseous Paget's Disease)	1) monostotic, 2) polyostotic, 3) non-classifiable/ unknown
Affected site ^{*2}	1) cranium, 2) vertebrae, 3) pelvis, 4) femur, 5) tibia, 6) other
Morbid period ^{*3}	1) <1 year, 2) ≥1 and <5 years, 3) ≥5 years, 4) unknown
Complication	1) none, 2) present, 3) unknown
Details of complication ^{*2*4}	1) hypertension, 2) diabetes mellitus, 3) hepatic disease, 4) cardiac disease, 5) renal disease, 6) gastrointestinal disease, 7) other
Medical history	1) none, 2) present, 3) unknown
Details of medical history ^{*2*4}	1) hypertension, 2) diabetes mellitus, 3) hepatic disease, 4) cardiac disease, 5) renal disease, 6) gastrointestinal disease, 7) other

Item	Category
Hypersensitivity	1) none, 2) present, 3) unknown
Details of hypersensitivity ^{*2}	1) drug, 2) food, 3) other, 4) unknown
Family history of osseous Paget's disease	1) none, 2) present, 3) unknown
Details of family history of osseous Paget's disease ^{*2}	1) father, 2) mother, 3) other, 4) unknown
History of fracture at the affected site	1) none, 2) present, 3) unknown
History of drug therapy for osseous Paget's disease ^{*5}	1) none, 2) present, 3) unknown
Details of history of drug therapy for osseous Paget's disease ^{*2*5*6}	1) calcitonin preparation, 2) etidronate, 3) this drug (Benet, Actonel), 4) bisphosphonate other than this drug and etidronate, 5) unknown
Concomitant drugs	1) none, 2) present, 3) unknown
Details of concomitant drugs ^{*2*6}	1) osteoporosis agents, 2) anti-inflammatory analgesic, 3) cardiac medication, 4) CNS agents, 5) diabetes medication, 6) gastrointestinal medication, 7) other

*1: not necessary for tabulation by patient unit.

*2: tabulate presence or absence for each category (duplicate tabulation)

*3: morbid period starts on the “day of initial diagnosis of osseous Paget's disease” and ends on the “day of starting administration of this drug”.

*4: classify disease names according to the MedDRA code

*5: include prior therapies in tabulation concerning the prior drugs for treatment of osseous Paget's disease.

*6: classify according to the JAPIC Code (drug data file)

2) List of onset of adverse drug reactions/infections (Attachment form 2 of the notification of Director of Ministry of Health, Labour and Welfare)

<Analysis population>

Patients included in safety evaluation.

<Preparation method>

Prepare according to (Note) 1 to 7 in Attachment form 2 of PFSB/ELD Notification No. 1027004 of Director of Pharmaceutical Evaluation Division dated October 27, 2005. Attach a list of adverse drug reactions/infections by patient unit to the far right of this table.

Prepare a list of onset of adverse drug reactions according to administration category (initial administration, re-administration 1, re-administration 2, re-administration 3 onward) and treatment period (≤ 56 days, ≥ 57 days, unknown) in the same manner shown in Attachment form 2.

Accumulation and total section in (Note) 2

- The same site participating in Ph 2 and Ph 3 is counted once concerning the number of surveyed sites up to approval.
- A report submitted by the same site for the first and second reporting is counted once concerning

cumulative total section for the number of surveyed sites.

- A report submitted from the same site prior to approval and during a special drug use survey is counted once concerning a total section of a number of surveyed sites.

Number of occurrences of same adverse drug reactions/infections encountered in the same patient in (Note) 3

- In tabulation of SOC, several occurrences of the same SOC in a given patient is counted once.
- In tabulation of PT, several occurrences of the same PT in a given patient is counted once.

Infections in (Note) 7

- No infection was collected or reported by the time of obtaining approval.

Percentage (%) of number of onset (occurrence) of adverse drug reactions by types in (Note) 7

- Calculate percentage (%) for the number of patients by types (occurrences) to the second decimal place (round up to the second decimal place). The same is applied hereinafter unless otherwise stated.

3) List of occurrences of serious adverse events (Attachment form 10 of the notification of Director of Ministry of Health, Labour and Welfare)

<Analysis population>

Patients included in safety evaluation.

<Preparation method>

Prepare according to (Notes) 1 to 8 in Attachment form 10 of PFSB/ELD Notification No. 1027004 of Director of Pharmaceutical Evaluation Division dated October 27,2005. Present serious adverse events by patient unit at the far right of this table.Cumulative total and total section in (Note) 3

- The same site that participates in Ph 2 and Ph 3 studies is counted once concerning the number of surveyed sites up to approval.
- A report submitted by the same site for the first and second reporting is counted once concerning cumulative total section for the number of surveyed sites.
- A report submitted from the same site prior to approval and during a special drug use survey is counted once concerning a total section of a number of surveyed sites.

Number of adverse events encountered in the same patient in (Note) 4

- In tabulation of SOC, several occurrences of the same SOC in a given patient is counted once.
- In tabulation of PT, several occurrences of the same PT in a given patient is counted once.

4) List of seriousness, date of onset, outcome of adverse drug reactions

<Analysis population>

Patients included in safety evaluation.

<Preparation method>

Tabulate seriousness, date of onset, and outcome of adverse drug reactions by types according to the category in the following table (2). Adverse drug reactions will be handled according to the “2) List of onset of adverse drug reactions/infections (Attachment form 2 of the notification from director of MHLW)”. However, in case of several occurrences of adverse drug reactions classified into the same PT in a given patient, select the most serious for seriousness, initial onset for the date of onset of adverse drug reactions, and the severest outcome.

Seriousness: serious>non-serious

Time of onset: event with earlier onset

Outcome: death> recovered with sequela> not recovered> improved> recovered >unknown

Prepare a list of adverse drug reactions according to administration category (initial administration, re-administration 1, re-administration 2, re-administration 3 onward) and treatment period (≤ 56 days, ≥ 57 days) in the same manner

Table (2) Category of seriousness, date of onset, and outcome

Item	Category
Seriousness	1) serious, 2) non-serious, 3) unknown
Timing of onset ^{*1}	1) Day 1 - 7, 2) Day 8 - 14, 3) Day 15 - 21, 4) Day 22 - 28, 5) Day 29 - 56, 6) Day 57 - 84, 7) Day 85 - 180, 8) Day 181 - 210, 9) Day 211 - 360, 10) Day 361 onward, 11) unknown
Outcome	1) recovered, 2) improved, 3) not recovered, 4) recovered with sequela, 5) death, 6) unknown

*1: number of days counted from the “date of starting administration” as “Day 1” until “date of onset of adverse drug reactions”.

5) Onset of adverse drug reactions by factors

<Analysis population>

Patients included in safety evaluation.

<Preparation method>

